#### 16.1.1. ALL AES

TEAEs will be summarized by System Organ Class (SOC) and Preferred Term (PT) for SEP-363856 (Overall). Listings of pre-treatment events and TEAEs will also be presented for all subjects enrolled. A listing of pre-treatment events will also be presented for screen failures.

TEAEs will also be summarized by SOC, PT and dose at event onset for SEP-363856 (Overall).

#### **16.1.2.** AEs Leading to Discontinuation of Study Medication

AEs leading to permanent discontinuation of study medication will be identified by using the AE page of the electronic case report form [eCRF], where "Action Taken with Study Treatment" is answered as "Drug Withdrawn". TEAEs will be summarized by SOC and PT for SEP-363856 (Overall). A listing of TEAEs leading to permanent discontinuation of study medication will be presented for all subjects enrolled.

#### 16.1.3. AEs Leading to Discontinuation from Study

AEs leading to permanent discontinuation from the study will be identified by using the AE page of the electronic case report form [eCRF], where "Caused Study Discontinuation" is answered as "Yes". TEAEs will be summarized by SOC and PT for SEP-363856 (Overall). A listing of TEAEs leading to permanent discontinuation from the study will be presented for all subjects enrolled.

#### 16.1.4. SEVERITY OF AES

Severity is classed as mild/moderate/severe (increasing severity). AEs with a missing severity will be classified as severe. If a subject reports an AE more than once within a SOC/ PT, the AE with the worst case severity (i.e., maximum severity) will be used in the summary.

TEAEs by severity will be summarized by SOC and PT for SEP-363856 (Overall).

#### **16.1.5. Relationship to Study Medication**

Relationship, as indicated by the Investigator, is classed as not related, possible, probable, or definite (increasing strength of relationship). A related AE is defined as an AE with a relationship to study medication as possible or probable or definite. AEs with a missing relationship to study medication will be regarded as related to study medication. If a subject reports an AE more than once within a SOC/ PT, the AE with the strongest relationship to study medication will be used in the summary.

TEAEs by relationship to study medication will be summarized by SOC and PT for SEP-363856 (Overall).

Document:	It: \\quintiles.net\enterprise\Apps\sasdata\SASa\sas\Sunovion\SEP- 363856\BZA44200\Biostatistics\Documentation\SAP\V1\SEP361-301 SAP Final V1.0_26JUL2023					
Author:		Version Number:	Final 1.0			
		Version Date:	26JUL2023			
Template No.:	CS_TP_BS016 Revision 5	Reference: 0	CS_WI_BS005			

Effective Date: 01Apr2018

Sumitomo Pharma PROTOCOL SEP361-118

Statistical Analysis Plan

#### **16.1.6. SERIOUS ADVERSE EVENTS**

Serious adverse events (SAEs) are those events recorded as "Serious" on the Adverse Events page of the (e)CRF. Serious TEAEs will be summarized by SOC and PT for SEP-363856 (Overall). A listing of serious TEAEs will be presented for all subjects enrolled.

#### **16.1.7.** Adverse Events Leading to Death

AEs leading to death are those events which are recorded with an AE outcome of "Fatal" on the Adverse Events page of the (e)CRF. A listing of TEAEs leading to death will be presented for all subjects enrolled.

#### 16.1.8. ADVERSE EVENTS OF POTENTIAL DRUG ABUSE AND DEPENDENCE

AEs of potential drug abuse and dependence are defined as the following PT: All PTs within the FDA Guidance for Industry: Assessment of Abuse Potential of Drugs (CDER 2017), all PTs listed in the MedDRA version 22.0 broad SMQ for Drug abuse and dependence [20000101], and all Pts listed in the FDA FMQ: Study Agent Abuse Potential, Broad (2022). The list of such PTs are found in APPENDIX 6. A listing of TEAEs of potential drug abuse and dependence will be presented for all subjects enrolled.

### **16.2.** LABORATORY EVALUATIONS

Results from the local laboratory will be included in the reporting of this study for hematology, serum chemistry, urinalysis, lipid panel, thyroid panel, urine drug screening, serology panel (hepatitis B Ag, hepatitis C Ab, and HIV Ab), coagulation panel and other tests [Serum Pregnancy ( $\beta$ -hCG) (in female subjects only), urine pregnancy test (in female subjects only), follicle stimulating hormone (FSH) (in female subjects only)]. A list of laboratory assessments to be included in the tables and listings is included in 0.

Hematology, serum chemistry (except HbA1c), urinalysis, and lipid panel laboratory tests data are collected at Visit 1 (screening), Visit 2 (Day -2), Visit 2 (Week 2), Visit 3 (follow-up) and ET (early termination). Urine drug screening is performed at Visit 1(screening), Visit 2 (Day -2), Visit 2 (Day -2), Visit 2 (Day 1), Visit 2 (Week 2), Visit 3 (follow-up) and ET (early termination). Serology panel, thyroid panel, HbA1c, and coagulation panel are collected at screening only.

Presentations will use standard international (SI) Units. Quantitative laboratory measurements reported as "< X", i.e. below the lower limit of quantification (BLQ), or "> X", i.e. above the upper limit of quantification (ULQ), will be converted to X for the purpose of quantitative summaries, but will be presented as recorded, i.e. as "< X" or "> X" in the listings.

The following summaries and listings will be provided for laboratory data:

• For laboratory parameters with continuous outcomes (serum chemistry, hematology, urinalysis and lipid panel), descriptive statistics (number of subjects, mean, standard deviation, median, Q1, Q3, minimum, and maximum) for the actual values and for changes from baseline (when post-baseline assessments are scheduled) will be presented at each scheduled timepoint for SEP-363856 (Overall). For thyroid panel and coagulation panel, descriptive statistics (number of subjects, mean, standard deviation, median, Q1, Q3,

Document:	\\quintiles.net\enterprise\Apps\sasdata\SASa\sas\Sunovion\SEP- 363856\BZA44200\Biostatistics\Documentation\SAP\V1\SEP361-301 SAP Final V1.0_26JUL2023				
Author:		Version Number:	Final 1.0		
		Version Date:	26JUL2023		
Template No.	Template No.: CS_TP_BS016 Revision 5 Reference: CS_WI_BS005				

Effective Date: 01Apr2018

minimum, and maximum) for the actual values will be presented at each scheduled timepoint for SEP-363856 (Overall). Glucose and lipid panel results will be summarized separately by fasting status: fasting only and overall (fasting, non-fasting, or fasting status unknown combined). Change from baseline for glucose and lipid panel results will only be calculated if post-baseline fasting status is matching baseline fasting status.

- For laboratory parameters with categorical outcomes (urinalysis and urine drug screening), the number and percentage of subjects with each outcome will be presented at each scheduled timepoint for SEP-363856 (Overall).
- Shift in lab results (serum chemistry (except HbA1c), hematology, urinalysis and lipid panel) from baseline to each post-baseline visit according to the reference range criteria provided by the local laboratory.
- The number and percentage of subjects with Sponsor-defined potentially clinically significant (PCS) laboratory values (serum chemistry, hematology, urinalysis and lipid panel) will be summarized for SEP-363856 (Overall) at each visit and overall post-baseline. For the individual visits, percentages will be calculated based on the number of safety population subjects with data available for the given parameter and at the given visit. For the overall post-baseline period, percentages will be calculated based on the number of safety population subjects who had at least one non-missing post treatment test results for a particular laboratory parameter. Any early termination visit, follow-up visit or unscheduled visit that occurs after first dose will be included in the period of evaluation for PCS post-baseline.

Data listings for all laboratory parameters (serum chemistry, hematology, urinalysis, lipid panel, thyroid panel, urine drug screening, serology panel, coagulation panel and other tests) will be provided for all subjects enrolled. Results outside of the reference range will be flagged.

A listing of Potentially Clinically Significant (PCS) laboratory findings (serum chemistry, hematology, urinalysis, lipid panel, thyroid panel and coagulation panel) will be presented for all laboratory parameters with PCS criteria defined for all subjects enrolled.

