a Subjects who screen fail may be re-screened up to two times, if judged appropriate by the Investigator. Subjects who screen fail due to MRI or PET or fMRI results may not be re-screened. Screening procedures will occur on multiple days. If subject re-screened, an MRI (without any abnormality) obtained at the study's imaging center within 90 days prior to Day -1 check-in is acceptable for eligibility.

b Extension of in-clinic stay during the screening phase to complete screening assessments may be allowed on a case-by-case basis with pre-approval of the Medical Monitor. Subject must be admitted to the clinic by Day -2.

c Dispensation of study drug on Day 1 and Day 8. All study drug will be taken once daily by mouth from Day 1 through Week 2 (Day 14). After 3 days of treatment with 50 mg/day SEP-363856, subjects are required to titrate up to 75 mg/day. Subjects may dose reduce one time to 50 mg/day for tolerability reasons at any time. Subjects who have a dose reduction for tolerability will continue to receive the reduced dose for the remainder of the study. The final dose, on Day 14, should occur approximately 2 to 4 hours prior to the final PET scan.

d The SCID-CT will be used to support the DSM-5 diagnosis and must be administered by a qualified rater with at least 2 years' experience with the population under study.

e Vital signs will include supine and standing measurements of blood pressure and heart rate, respiratory rate, and oral body temperature.

f Subjects must be fasted (no food or drink except water at least 8 hours prior to specified blood tests). Blood samples should be drawn in the morning followed by a snack or meal.

g Blood samples for follicle stimulating hormone (FSH) will be collected if menopause is suspected.

h Any positive urine  $\beta$ -hCG test should be confirmed by a serum  $\beta$ -hCG test. Must be performed prior to PET scan on same day as screening scan and on Day 14 scan.

i Blood samples for determination of SEP-363856 and SEP-363854 concentrations will be collected on Day 1 (approximately 10 minutes prior to dosing), Day 2 (2 – 4 hours postdose), Day 7 (2 – 4 hours postdose), Day 14 (prior to PET scan), and at Follow-up.

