### 7.2. **BASELINE**

Unless otherwise specified, baseline is defined as the last non-missing measurement taken prior to the first dose of study medication (including unscheduled assessments). Whenever available, the time information should be accounted for in the derivation of baseline values. In the case where time is not available and the date of the last non-missing measurement and the date of the first dose of study medication coincide, that measurement will be considered baseline.

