# 7.3. RETESTS, UNSCHEDULED VISITS AND EARLY TERMINATION DATA

In general, for by-visit summaries, data recorded at the nominal visit will be presented.

In the case of a retest, the assessment recorded under the planned visit will be used for by-visit summaries, and the assessment(s) recorded under unscheduled visit(s) will be presented in listings only.

Early termination data will be mapped to the next scheduled or planned timepoint where an assessment is expected to be performed as specified by the Schedule of Assessment table in the Protocol for by-visit summaries. This applies to all efficacy, safety, and PK data.

Listings will include scheduled, unscheduled, retest and early discontinuation data.

Unscheduled measurements will not be included in by-visit summaries. Unscheduled measurements collected prior to the first dose of study medication will contribute to the derivation of the baseline value. Unscheduled measurements collected post baseline will contribute to the derivation of potentially clinically significant (PCS) post-baseline value and worst case value where required.

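### Glucose and lipid baseline is chosen without regard to fasting, while change requires matching fasting status and shifts state no such condition; a usable fasted pair can be lost and a food effect can appear as a shift

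*SAP*

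**What the plan says.** **Baseline.** SAP 7.2 sets a general rule that applies unless a section says otherwise: "baseline is defined as the last non-missing measurement taken prior to the first dose of study medication (including unscheduled assessments"). SAP 7.3 repeats the point for extra samples: "Unscheduled measurements collected prior to the first dose of study medication will contribute to the derivation of the baseline value". SAP 16.2 sets no separate baseline for glucose or lipids.

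**Samples.** Two pre-dose draws are scheduled. In SAP 16.2, chemistry and "lipid panel laboratory tests data are collected at Visit 1 (screening), Visit 2 (Day -2"), then again at Week 2, Follow-up and early termination. Protocol Table 2, footnote f, on the glucose and lipid row, requires: "Subjects must be fasted (no food or drink except water at least 8 hours prior to specified blood tests"). Protocol Sections 11.9.1, 11.9.2.1, 11.9.2.6, 11.9.3 and 11.9.4 repeat the fasted condition for Screening, Day -2, Day 14, Follow-up and early termination.

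**Summaries and change.** SAP 16.2 summarizes glucose and lipids in two sets, "fasting only and overall (fasting, non-fasting, or fasting status unknown combined"). It then restricts change: "Change from baseline for glucose and lipid panel results will only be calculated if post-baseline fasting status is matching baseline fasting status".

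**Shifts.** A separate bullet in SAP 16.2 plans: "Shift in lab results (serum chemistry (except HbA1c), hematology, urinalysis and lipid panel) from baseline to each post-baseline visit", judged against the local laboratory's reference range. Glucose is a serum chemistry analyte in SAP Appendix 3, so it is included. This bullet mentions no fasting condition.

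**The concern.** The SAP foresees non-fasted and unknown-status results and treats a mismatch as invalid for change. The baseline rule does not follow from that. It can select a non-fasted value when an earlier fasted one exists, and the matching rule then sets the change to missing. SAP 7.8 allows no imputation.

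The shift bullet goes the other way. On its wording, a mismatch that disqualifies a subject from the change table does not disqualify the same subject, for the same analyte, from the shift table. A fasted normal baseline followed by a non-fasted post-dose sample can then be reported as Normal to High.

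Change from baseline in laboratory tests is a listed safety endpoint (SAP 3.2). The trial has one arm, so no control group would reveal a food effect, and one subject in 22 is 4.5%.

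**Working it through.** The plan states no figure on this point, so there is nothing to reproduce. The check is to apply the written rules to every fasting pattern.

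**Step 1: enumerate.** F is fasted and N non-fasted. Baseline is the Day -2 value (SAP 7.2, no unscheduled sample). Change is computed only if Day -2 and Week 2 match (SAP 16.2).

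| Screening | Day -2 | Week 2 | Change | Shift comparison |
|---|---|---|---|---|
| F | F | F | computed | matched |
| F | F | N | missing | unmatched |
| F | N | F | **missing, although a fasted pair exists** | unmatched |
| F | N | N | computed | matched |
| N | F | F | computed | matched |
| N | F | N | missing | unmatched |
| N | N | F | missing | unmatched |
| N | N | N | computed | matched |

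One pattern of eight loses a usable fasted pair, and four enter the shift table unmatched. A Day -2 sample of unknown status followed by a fasted Week 2 sample behaves like the third row.

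**Step 2: scale.** Planned N is 22 (Protocol 15.1). The documents give no rate of non-fasted draws, so assume an equal, independent probability p at each draw.

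- Usable pair lost at Week 2: (1-p) × p × (1-p) = p(1-p)²
- Unmatched shift comparison at Week 2: 2p(1-p)
- Of these, fasted baseline to non-fasted Week 2: p(1-p), one half

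| Assumed p | Lost pairs, 22 × p(1-p)² | Unmatched shifts, 22 × 2p(1-p) | Of which F to N |
|---|---|---|---|
| 0 | 0 | 0 | 0 |
| 2% | 22 × 0.0192 = 0.4 | 22 × 0.0392 = 0.9 | 0.4 |
| 5% | 22 × 0.0451 = 1.0 | 22 × 0.095 = 2.1 | 1.0 |
| 10% | 22 × 0.081 = 1.8 | 22 × 0.18 = 4.0 | 2.0 |
| 20% | 22 × 0.128 = 2.8 | 22 × 0.32 = 7.0 | 3.5 |

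The loss is greatest at p = 1/3: 22 × (1/3) × (4/9) = 3.3 subjects.

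**Step 3: read the shift column correctly.** These are unmatched comparisons, not false shifts. Only the F-to-N half runs in the direction where a meal could look like a drug effect, and only if the value crosses the reference limit. The other half can hide a rise or show a spurious return to normal.

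**Step 4: apply the change proposed below.** With the last confirmed-fasted pre-dose value as baseline, the third row yields a valid fasted change. In a fasting-only shift table, unmatched comparisons are zero by construction.

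**The case against.** The strongest reply is that fasting is required at every scheduled glucose and lipid draw, with morning sampling, and some subjects are already in-clinic before Day -2. If the protocol is followed, nothing is lost and nothing is unmatched. That stands, and it is why the point concerns what can happen. It does not close the gap. The SAP itself provides for non-fasted and unknown results. Unscheduled pre-dose samples feed the baseline. The fasting footnote is attached to the glucose and lipid row of Table 2, not the chemistry row, although glucose is also a chemistry analyte. Some subjects arrive from home on Day -2, and Follow-up is an outpatient visit.

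A second reply is that the SAP is silent on fasting in the shift tables and does not permit mismatches. The output templates (SAP 8), which are not in the documents, might add a restriction, and the laboratory's ranges might account for fasting. This also stands: the gap is an omission, but nothing in the text fills it.

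A third is that a near-dose baseline with some missing changes is preferable to an older one. A Screening sample can be up to 49 days before dosing. For an antipsychotic dosed within label, stability is required for 3 weeks before the screening PET scan, which may fall as late as Day -2. The stable period may therefore begin only at about Day -23 (2 + 21 days before dosing), after an early Screening sample. This is a real cost. It argues for flagging the fallback baselines, not for leaving the rule as it is.

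A reader might also infer that the potentially clinically significant (PCS) counts share the flaw. They do not: the Appendix 4 limits for these analytes are absolute (for example, glucose above 13.9 mmol/L), involve no baseline comparison, and may properly count all samples.

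**Conclusion.** The concern holds as a gap between SAP rules. Baseline selection ignores fasting, change requires a match, and the shift bullet states no match. Together they can drop a usable fasted pair and admit an unmatched shift for the same subject.

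Under equal, independent non-fasting at 5% to 20% per draw, the expected effect at Week 2 is about 1 to 3 lost pairs and 2 to 7 unmatched shift comparisons among 22 subjects. It is zero with full compliance. The rate is an assumption.

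Two stronger readings are not supported:

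- **Up to 7 of 22 subjects lose their change.** That figure is 22 × 0.30 = 6.6. It needs 30% failure at Day -2 with none at Screening or post-dose, although the same fasting instruction applies throughout. At an equal 30% per draw, the Week 2 loss is 22 × 0.3 × 0.49 = 3.2.
- **Two unknown statuses count as a match.** The SAP does not say so. It mentions unknown status only within the combined set. It does not exclude that reading either, so one sentence should settle it.

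Actual values are still summarized and listed. Only descriptive safety tables are affected, and the primary PET endpoint is untouched. Priority is low.

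**What to change.** In SAP 16.2, for glucose, LDL-cholesterol, HDL-cholesterol and triglycerides:

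1. Present shift tables in two sets, as already planned for the descriptive summaries: fasting only (baseline and post-baseline both confirmed fasted) and overall.
2. For the fasting-only change and shift, define baseline as the last confirmed-fasted pre-dose sample. Flag subjects whose baseline falls back to Screening. The overall set keeps the SAP 7.2 baseline.
3. State that unknown fasting status never counts as a match.

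Leave the PCS counts on all samples.

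The cost is a few lines of SAP text, one extra baseline derivation for four analytes and an additional set of shift tables. The downside is confined to affected subjects: their baseline may be up to 49 days old and may predate stabilisation of background medication, so they should be identifiable in the laboratory listing.

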#### 16.2.1. LABORATORY REFERENCE RANGES AND POTENTIALLY CLINICALLY SIGNIFICANT CRITERIA

Laboratory reference range indicators provided by the local lab will be used in statistical analyses. Only if a reference range indicator is missing in the data transfer will it be derived in the analysis step as described below.

- Quantitative laboratory measurements (that are not urinalysis erythrocytes or urinalysis leukocytes) will be compared with the relevant laboratory reference ranges in original units and categorized as:
  - Low: Below the lower limit of the laboratory reference range.
  - Normal: Within the laboratory reference range (upper and lower limit included).
  - High: Above the upper limit of the laboratory reference range.
- For qualitative laboratory measurements as well as urinalysis erythrocytes and urinalysis leukocytes, if the result is within the reference range, the indicator is "NORMAL"; if the result is not within range, the indicator is "ABNORMAL".

In addition, PCS laboratory values will also be identified in accordance with the Sponsor defined PCS criteria as presented in APPENDIX 4.

Document:	cument: \\quintiles.net\enterprise\Apps\sasdata\SASa\sas\Sunovion\SEP-					
	363856\BZA44200\Biostatistics\Documentation\SAP\V1\SEF	2361-301 SAP Final \	/1.0_26JUL2023			
Author:		Version Number:	Final 1.0			
		Version Date:	26JUL2023			
Template No.:	CS TP BS016 Revision 5	Reference: (	CS WI BS005			

Effective Date: 01Apr2018

Sumitomo Pharma PROTOCOL SEP361-118

Statistical Analysis Plan

Page 31 of 58

### **16.3. ECG EVALUATIONS**

Results from the central ECG (Electrocardiogram) Reading Centre will be included in the reporting of this study. The following ECG parameters will be reported for this study:

- PR Interval (msec)
- QRS Duration (msec)
- QRS Axis (deg)
- RR interval (msec).
- QT Interval (msec)
- QTcF Interval (msec)
- QTcB Interval (msec)
- HR (bpm)
- Overall assessment of ECG as determined by central over-read:
  - Normal
  - Abnormal, Insignificant
  - Abnormal, Significant
  - Not Evaluable
- ECG findings

Electrocardiogram parameters and changes in these parameters from baseline, as determined by the central overread, will be summarized using descriptive statistics (number of subjects, mean, standard deviation, median, Q1, Q3, minimum, and maximum) at each timepoint for SEP-363856 (Overall) for the safety population. For overall assessment, the number and percentage of subjects will be presented at each timepoint for SEP-363856 (Overall) for the safety population.

Shift in ECG overall assessments from baseline to each post-baseline visit will also be presented.

The number and percentage of subjects with QTcF/QTcB values in the following categories will be summarized:

- QTcF/QTcB > 500 ms at any postdose timepoint (including unscheduled visits) not present at baseline
- QTcF/QTcB > 480 ms at any postdose timepoint (including unscheduled visits) not present at baseline
- QTcF/QTcB > 450 ms at any postdose timepoint (including unscheduled visits) not present at baseline
- Change from baseline in QTcF/QTcB ≥ 60 ms for at least one postdose measurement (including unscheduled visits)
- Change from baseline in  $QTcF/QTcB \ge 30$  ms for at least one postdose measurement (including unscheduled visits) and < 60 ms for all postdose measurements (including unscheduled visits)

Document:	: \\quintiles.net\enterprise\Apps\sasdata\SASa\sas\Sunovion\SEP- 363856\BZA44200\Biostatistics\Documentation\SAP\V1\SEP361-301 SAP Final V1.0_26JUL2023				
Author:		Version Number:	Final 1.0		
		Version Date:	26JUL2023		
Template No.	: CS_TP_BS016 Revision 5	Reference:	CS_WI_BS005		

Effective Date: 01Apr2018

For the post-baseline summaries, the percent of subjects will be based on the number of safety population subjects with at least one non-missing post treatment value. For the change from baseline summaries, percentages will be based on the number of subjects with both baseline and at least one post-baseline result available. Any early termination visit, follow-up visit or unscheduled ECG that occurs after first dose will be included for these post treatment summaries.

Data listings for all ECG parameters will be provided for all subjects enrolled.

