  - d. Subject currently has or has had within the last 6 months a diagnosis of Alcohol or Substance Abuse Disorder (DSM-5 criteria). The only exceptions include caffeine or nicotine.
  - e. Subject has a clinically significant abnormal 12-lead ECG that may jeopardize the subject's ability to complete the study as determined by the Investigator or a screening 12-lead ECG demonstrating any one of the following: heart rate > 100 beats per minute, QRS > 120 ms, QT interval corrected for heart rate using Fridericia's formula (QTcF) > 450 ms (males), QTcF > 470 ms (females), or PR > 220 ms.
  - f. Subjects with known history of human immunodeficiency virus (HIV) seropositivity.
  - g. Subject has a history of clinically significant hypotensive disorder, systolic blood pressure  $\leq$  80 mmHg or diastolic blood pressure  $\leq$  40 mmHg at any measurement prior to dosing on Day 1, or any clinically significant symptoms associated with hypotension at any time during participation prior to dosing on Day 1
7. Female subject who is pregnant or lactating.
8. Subject has a presence or history of a medically diagnosed, clinically significant psychiatric disorder (including intellectual disability, major depressive disorder with psychosis, and bipolar disorder) other than schizophrenia (medically diagnosed schizoaffective disorder or schizopreniform disorder will be allowed).
9. Subject tests positive for drugs of abuse at screening, however, a positive test for barbiturates, opiates, benzodiazepines or methadone may not result in exclusion of subjects if the Investigator determines that the positive test is as a result of prescription medicine(s). In the event a subject tests positive cannabinoids (tetrahydrocannabinol), the Investigator will evaluate the subject's ability to abstain from using this substance during the study. This information will be discussed with the Medical Monitor prior to study enrollment.
10. Subject is at significant risk of harming him/herself or others according to the Investigator's judgment.
11. Subject has attempted suicide within 6 months prior to screening.

12. Subject is involuntarily hospitalized.
13. Subject is judged in the opinion of the Investigator to be severely resistant to antipsychotic treatment defined as a failure to respond to 4 or more marketed antipsychotic agents, given at an adequate dose as per labeling and for an adequate duration (lifetime).

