#### **15.3.8.3. Electrocardiograms**

Electrocardiogram parameters to be collected include ventricular heart rate, QT interval, PR interval, QRS duration, and RR interval (ms). The corrected QT interval will be derived according to the Fridericia formula (QTcF) as well as Bazett’s formula (QTcB).

ECG data will be summarized overall for the safety population.

Electrocardiogram parameters and changes in these parameters from baseline, as determined by the central over-read, will be summarized using descriptive statistics (number of subjects, mean, standard deviation, median, minimum, and maximum) at each visit.

The number and percentage of subjects with QTcF values in the following categories will be summarized:

- QTcF  $\geq$  500 ms at any postdose timepoint and not present at baseline.
- QTcF  $\geq$  480 ms at any postdose time point and not present at baseline.
- QTcF  $\geq$  450 ms at any postdose timepoint and not present at baseline.
- Change from baseline in QTcF  $\geq$  60 ms for at least one postdose measurement.
- Change from baseline in QTcF  $\geq$  30 ms for at least one postdose measurement, but  $\leq$  60 ms for all postdose measurements.

For these categorical analyses, the percent of subjects will be based on the number of subjects with at least one non-missing post treatment value. Any early termination visit or unscheduled ECG that occurs after the single dose will be included for these posttreatment summaries.

The number and percentage of subjects with potentially clinically significant post-baseline values (defined in the SAP) will be presented.

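### The QTc threshold rows in SAP 16.3 count only new exceedances but divide by everyone with a post-dose ECG, a small dilution that matters in practice only for QTcB > 450 ms

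*SAP*

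**What the plan says.** SAP 16.3 (ECG Evaluations) lists three threshold rows for both heart-rate corrections: "QTcF/QTcB > 450 ms at any postdose timepoint (including unscheduled visits) not present at baseline", and the same wording at 480 ms ("QTcF/QTcB > 480 ms at any postdose timepoint (including unscheduled visits) not present at baseline") and 500 ms ("QTcF/QTcB > 500 ms at any postdose timepoint (including unscheduled visits) not present at baseline"). It then gives two denominator rules. The first governs post-baseline results, and so the threshold rows: "the percent of subjects will be based on the number of safety population subjects with at least one non-missing post treatment value". A second rule governs the rows for increases of 30 and 60 ms over baseline: "percentages will be based on the number of subjects with both baseline and at least one post-baseline result available".

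Protocol 15.3.8.3 sets the same denominator for its categories: "the percent of subjects will be based on the number of subjects with at least one non-missing post treatment value". Those categories are QTcF only, as is the replacement text in SAP 4.2. The extension to QTcB appears first in SAP 16.3.

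Exclusion 6e (Protocol 8.2) limits the screening ECG. It bars a heart rate above 100 beats per minute, QTcF above 450 ms in men, and, at the end of the list, "QTcF > 470 ms (females), or PR > 220 ms". There is no QTcB limit. Under SAP 7.2, baseline is the last available value before the first dose, and Protocol 11.9.2.3 schedules an ECG on Day 1 before dosing.

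**The concern.** The numerator removes subjects already above a threshold at baseline and the denominator keeps them. The row is therefore a share of all assessed subjects, while its wording invites a reader to take it as the rate at which subjects newly exceeded the threshold. The study has one arm, so no control group carries the same dilution. When the discrepancy has any effect, it makes the row look slightly more favourable. The ECG shift table that SAP 16.3 plans covers the overall normal/abnormal assessment, not QTc category, so a reader who wanted the at-risk number would have to count it from the listings.

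**Working it through.** **Inputs from the documents.** The numerator and denominator rules are those of SAP 16.3 and the entry limits those of exclusion 6e. The planned size is 22 (Protocol 15.1). That figure reproduces: 16 completers with 25% drop-out gives 16/0.75 = 21.3, rounded up to 22. The documents state no expected QTc incidence.

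**Dilution formula.** Let N be subjects with a post-dose ECG, b those above the threshold at baseline and x the new cases. Then

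- reported % = x/N
- at-risk % = x/(N − b)
- reported/at-risk = (N − b)/N

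The ratio is 1 when b = 0 and below 1 otherwise. If x = 0, both percentages are zero.

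**Other reading of the denominator.** If the threshold rows fell under the change-from-baseline rule, the denominator would need a baseline and a post-baseline value. That still keeps everyone whose baseline is above the threshold, so the mismatch remains.

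**Can b exceed zero under the entry limits?** From the standard Bazett and Fridericia formulas (named in the protocol but not written out), QTcB = QTcF × (HR/60)^(1/6). At 80 bpm the factor is (80/60)^(1/6) = 1.0491, so QTcB exceeds 450 ms once QTcF exceeds 450/1.0491 = 428.9 ms.

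| Heart rate (bpm) | QTcF giving QTcB 450 ms | Highest eligible QTcB, men / women (ms) |
|---|---|---|
| 75 | 433.6 | 467.1 / 487.8 |
| 80 | 428.9 | 472.1 / 493.1 |
| 90 | 420.6 | 481.5 / 502.9 |
| 100 | 413.3 | 490.0 / 511.8 |

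An eligible subject can therefore start above QTcB 450 ms at ordinary heart rates. Starting above 480 ms takes a high QTcF, a fast heart rate or both, and starting above 500 ms is possible only at the extreme for women. For QTcF, only women above 450 and up to 470 ms, plus any upward drift after screening, can start above 450 ms. At the screening limits nobody starts above 480 or 500 ms.

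**How many might start above?** The documents do not say, so this step is assumption throughout. Assumed: mean QTcF 405 ms (men) and 415 ms (women), between-subject SD 16 ms, visit-to-visit SD 9 ms, 70% men, mean heart rate 78 bpm with SD 10 between and 6 within subjects, and no drug effect. The entry limits apply to a screening ECG, followed by one baseline and two post-dose ECGs.

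- QTcB > 450 ms, base case: 12.9% start above, about 3 of 22. Incidence is 9.6% with the SAP denominator and 11.0% at risk. Check: 11.0% × (1 − 0.129) = 9.6%.
- QTcB > 450 ms, varying mean QTcF by ±5 ms, mean heart rate over 72–84 bpm and between-subject heart-rate SD over 8–12 bpm together: roughly 5% to 25% start above.
- QTcB > 480 ms, same range: under 2% start above.
- QTcF > 450 ms, same range: about 0.6% to 2% start above, or well under one subject in 22. The > 480 and > 500 ms QTcF rows are smaller still.

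**What this does to a row with N = 22** (b and x are illustrative):

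| b | x | Reported | At risk | Ratio |
|---|---|---|---|---|
| 0 | 3 | 13.6% | 13.6% | 1.000 |
| 1 | 2 | 9.1% | 9.5% | 0.955 |
| 2 | 2 | 9.1% | 10.0% | 0.909 |
| 3 | 3 | 13.6% | 15.8% | 0.864 |
| 4 | 3 | 13.6% | 16.7% | 0.818 |

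For b from 1 to 4 with two or three cases, the shift runs from 0.4 to 3.0 percentage points.

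**The case against.** The strongest reply is that new exceedances over all assessed subjects is a legitimate, pre-specified quantity. It is understated only if the at-risk proportion is the target, and neither document names that target. The SAP keeps the protocol's denominator here, and its overall post-baseline tables for laboratory values and vital signs also divide by subjects with a post-treatment value. This stands as a reason to call the point an improvement and not an error against the protocol.

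It is also fair that the effect is nearly invisible. Counts sit beside the percentages and all ECG data are listed. A subject already above 450 ms who worsens can still appear in a higher threshold row or in the 30 or 60 ms change rows. Exact 95% intervals for 3/22 (2.9% to 34.9%) and 3/19 (3.4% to 39.6%) overlap almost entirely. No test or stopping rule uses these rows.

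A reader might infer that SAP 16.3 contradicts itself because its change rows already use an evaluable-subject denominator. The text does not support that. The rule requires both values because a change cannot otherwise be computed, and it excludes nobody for a high baseline.

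What survives is the mismatch itself, which both readings of the denominator sentence leave in place, and the fact that the one row with a noticeable effect was added by the SAP under a denominator written for QTcF.

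**Conclusion.** The point holds as a cheap improvement. The direction follows from the text alone: the at-risk percentage is never overstated, and it is understated when someone starts above the threshold and someone else becomes a new case. The size does not follow from the text. It rests on the assumed QTc and heart-rate distributions, under which roughly 5% to 25% of subjects start with QTcB > 450 ms and the row moves by one to a few percentage points. For the QTcF rows the effect is negligible.

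Two stronger readings go too far. One is that the table will always make the drug look safer: with no baseline exceedance or no new case, nothing changes. The other is that a QT signal would be hidden: the counts, change rows, by-visit summaries and listings are unaffected, and no decision rests on the percentage.

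**What to change.** In SAP 16.3, replace the denominator sentence for the threshold rows with, for example: *For each QTcF and QTcB threshold row, percentages are based on safety-population subjects with a non-missing baseline value at or below that threshold and at least one non-missing post-dose value.* Leave the 30 and 60 ms rows as they are. Show the n for each row in the table or in a footnote; SAP Appendix 5 (Denominators) allows either. List the departure from Protocol 15.3.8.3 in SAP 4.2, and mention there that the categories now also cover QTcB.

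The sentence also settles a case the SAP leaves open: how to class a subject with no baseline ECG.

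The cost is one sentence, one entry in SAP 4.2 and an n row or footnote. The nested 450/480/500 ms rows will have different denominators, subjects without a baseline ECG drop out of them, and some percentages become slightly less favourable. If the sponsor prefers to keep the protocol's denominator, a row giving the number above each threshold at baseline, among those with a post-dose ECG, would carry nearly the same information.
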